8. GENERAL ANAYLSIS AND REPORTING CONSIDERATIONS

Descriptive summaries will be provided where appropriate for each of the primary and secondary variables. In general, tables will summarize data by treatment group and visit.

Continuous, quantitative variable summaries will include the number of patients (N) with non-missing values, mean, standard deviation, median, minimum, and maximum.

[figure not shown]
Categorical, qualitative variable summaries will include the frequency and percentage of patients who are in the particular category. In general, the denominator for the percentage calculation will be based upon the total number of patients in the study population for the treatment group unless otherwise specified.

Unless otherwise specified, baseline values are defined as the last non-missing measurement prior to the first dose of study drug. Change from baseline will be defined as the post-baseline visit value minus the baseline value.

For continuous endpoints where treatment groups are compared via linear models with the difference in LS means, the effect size will be calculated and included as a summary statistic using the difference in LS means and its standard error, transformed to a standard deviation. Study day is defined as assessment date – first dose date +1 for dates after the first dose date and assessment date – first dose date for dates prior to the first dose.

All analyses will be performed using SAS® Software version 9.4 or later.

8.1.1. Study Success

8.1.2. Multicenter Studies

This is a multicenter study. Unless otherwise specified, data from all study sites will be pooled for all analyses unless otherwise specified.

8.1.3. Assessment Time Windows

Patients who withdraw/drop out from the study will have the early termination (ET) data collected at their ET visit included in the analysis at the closest visit where a given assessment should be collected per the schedule of assessments (Week 2, 4, 6), using midpoints between

Statistical Analysis Plan: TNX-TI-M201

visits to window the early termination. If this results in two records for a given visit, then the scheduled visit will be used, followed by the record closest to the targeted date. See section 10.5.4.3 for details specific to the SOWs windowing.

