10.3. Visits 3 and 4 (Weeks 2 through 4)

Visits 3 and 4 are similar study visits that are scheduled to be conducted after 2 and 4 weeks of treatment, respectively. Visit 3 should occur on Day 15 ± 2 days and Visit 4 should occur on Day 29 ± 2 days.

The following assessments and procedures are scheduled for these visits in the following general order:

- Collect study drug and assess compliance and accountability
- Assess occurrence of AEs
- Update concomitant medications
- Obtain vital signs and weight
- Review placebo response training with patient
- Administer the MADRS
- Conduct urine pregnancy test (for women of child-bearing potential)
- Visit 4 only: Draw samples, fasting or non fasting, for clinical laboratory tests for:
 - Chemistry and hematology
 - o PK
- Have the patient complete the following outcome scales (in order):
 - o SDS
 - o PGIS
 - o PGIC
- Administer the HARS
- Administer C-SSRS Since Last Visit Version
- Administer MADDERS[®] only if any pre-defined AEs and/or Drug Accountability Discrepancy Events (DADE) suspect for misuse, abuse, or diversion event is identified
- Investigator to assess CGI-S and CGI-I (needs to be completed once all other assessments are available for Investigator to review)

• Dispense new bottle of double-blind study drug as assigned by IWRS

After all assessments at each visit have been completed, the patient should be given an appointment to return to the clinic for the next scheduled visit, and be re-instructed, as necessary, on dosing instructions, and reminded to bring study drug back to the clinic at their next visit.

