10.4. Visit 5 (Week 6)

End of Treatment (Visit 5) should occur after 6 weeks of double-blind study drug treatment, scheduled at Day 43 + 2 days. The following assessments and procedures are to be completed in the following general order:

- Collect study drug and assess compliance and accountability
- Assess occurrence of AEs
- Update concomitant medications
- Obtain information on current use of alcohol, nicotine/tobacco (smoking, vaping and/or chewing), and marijuana
- Perform physical examination, including a brief neurological examinationObtain vital signs and weight
- Review placebo response training with patient
- Administer MADRS
- Conduct urine pregnancy test (for women of child-baring potential). Serum pregnancy test may be done at Investigator's discretion.
- Draw samples, fasting or non-fasting, for clinical laboratory tests for:
 - Chemistry and hematology
 - o PK
- Conduct 12-lead ECG
- Have the patient complete the following outcome scales (in order):
 - o SDS
 - PGIS, PGIC
 - o CSFQ-14
- Administer the HARS
- Administer C-SSRS-Since Last Visit Version
- Administer SOWS and train the patient on how to report the SOWS at Day +1, +2, +3, +6, +9 and +12 days via the IWRS
- Administer MADDERS[®] only if any pre-defined AEs suspect for misuse, abuse, or diversion event is identified, or any drug accountability issues above the pre-defined threshold is identified

- Physician to assess CGI-S and CGI-I (needs to be completed once all other assessments are available for Investigator to review)
- Schedule the Post Study Follow-up (Visit 6)

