11.3.4. Vital Signs, Height, and Weight

Vital signs including sitting or supine blood pressure, heart rate, temperature, and weight will be assessed at Visit 1 (Screening), Visit 2 (Baseline), and Visits 3, 4 and 5/ET (after 2, 4, and 6 weeks of treatment, respectively), as well as at Visit 6. Height will be measured without shoes at Screening (Visit 1) only. The BMI will be a derived variable, based on height and weight entries. A BMI of <18.0 or >40.0 kg/m² is an exclusion criterion. Blood pressure and heart rate should be measured after sitting or supine for five minutes at rest. Height will be measured without shoes at Screening (Visit 1) only. The BMI will be a derived variable, based on height and weight entries. A BMI of <18.0 or >40.0 kg/m² is an exclusion criterion. Blood pressure and heart rate should be measured after sitting or supine for five minutes at rest. Height will be measured without shoes at Screening (Visit 1) only. The BMI will be a derived variable, based on height and weight entries. A BMI of <18.0 or >40.0 kg/m² is an exclusion criterion.

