10.4. Clinical Laboratory Evaluation

Laboratory data including Chemistry, Hematology, and urinalyses will be summarized by treatment and visit for the Safety Population. Descriptive summaries of actual values and changes from baseline will be presented by study visit for each clinical laboratory analyte and for each treatment group. 95% confidence intervals will be presented for change from baseline.

Laboratory values will be displayed in the data listings with their corresponding normal ranges, and those values that are outside the normal range will be flagged

Results of urine drug screens and pregnancy tests will be presented in listings.

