10.5.4.2. Changes from baseline in the Sexual Functioning Questionnaire Short-Form (CSFQ-14)

The CSFQ-14 will be analyzed by gender. Note: there is a male version and female version for the CSFQ-14. Descriptive summaries (mean, SD, median, minimum, and maximum) of actual values and changes from baseline at each assessment time point and last on-treatment assessment will be calculated for each CSFQ domain score and the total. Note that the CSFQ is considered both an efficacy and safety endpoint.

Statistical Analysis Plan: TNX-TI-M201

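### Early-termination vital signs and laboratory values taken within about 7 days after an attended visit enter no value table; a last on-treatment row would bring them back

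*SAP*

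**What the plan says.** SAP 8.1.3 (Assessment Time Windows) states that ET data are "included in the analysis at the closest visit where a given assessment should be collected per the schedule of assessments (Week 2, 4, 6"), with the boundaries set "using midpoints between" visits. When an ET record and a scheduled record land in the same visit, "If this results in two records for a given visit, then the scheduled visit will be used". The section stands under the general reporting considerations and is worded for any assessment. Only the SOWS has its own windowing rule.

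The visit days come from the protocol. Section 10.3: "Visit 3 should occur on Day 15 ± 2 days and Visit 4 should occur on Day 29 ± 2 days". Section 10.4 has Visit 5 "scheduled at Day 43 + 2 days". Vital signs are taken at Visits 1 and 2, "and Visits 3, 4 and 5/ET (after 2, 4, and 6 weeks of treatment, respectively), as well as at Visit 6" (section 11.3.4). After baseline, chemistry and hematology are drawn only at Week 4 and at Week 6 or ET (section 11.3.6).

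For laboratory data, SAP 10.4 says: "Descriptive summaries of actual values and changes from baseline will be presented by study visit". SAP 10.5.1 does the same for vital signs at each time point. Neither section plans a last-value, worst-value or shift table. By contrast, SAP 10.5.4.2 plans for CSFQ-14 that "changes from baseline at each assessment time point and last on-treatment assessment will be calculated".

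**The concern.** Take a patient who attends Visit 4 on Day 29 and has an ET visit on Day 33. Both records belong to Week 4. The Day 29 values are tabulated. The Day 33 values drop out of the mean, the median, the minimum and the maximum, and no other value table picks them up.

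The ET visit exists largely for safety. Protocol 7.1 asks withdrawing patients to attend it for safety evaluation, and section 10.4.1 prefers that it take place before a substantial lapse in study drug. Safety and tolerability are the secondary objective. A laboratory set taken at ET on Days 30-36 is the later of only two on-treatment sets for that patient, and it is the one that the rule sets aside. At stake is whether the by-arm laboratory and vital-sign tables represent patients at the point where they stop.

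**Working it through.** The documents state no share of ET records lost and no ET rate or timing, so there is no plan figure to reproduce. The check applies the rule directly.

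**Inputs.** Target days are 15, 29 and 43 for vital signs; 29 and 43 for laboratory values; 43 only for ECG on treatment (protocol 11.3.5). The base case assumes that ET timing is uniform over Days 1-43, a span of 42 days, and that earlier scheduled visits were attended.

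**Midpoints.** (15 + 29)/2 = 22 and (29 + 43)/2 = 36. Each lies 7 days after the nominal visit. With the ±2-day visit windows, the reach from the actual visit is 5 to 9 days.

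**Displaced ET days.**
- Vital signs: Days 16-22 and 30-36, 7 + 7 = 14 days. An ET before Visit 3 goes to Week 2, has no competing record and is kept.
- Laboratory values: Days 30-36, 7 days. An ET before Visit 4 goes to Week 4 unopposed and is kept.
- ECG: none.

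**Shares under uniform timing.**
- Vital signs: 14/42 = 33% of all ETs. Among ETs after Week 2, 14/28 = 50%.
- Laboratory values: 7/42 = 17% of all ETs. Among ETs after Week 4, 7/14 = 50%.
- The SAP does not say where an ET exactly on Day 22 or 36 goes. If both days moved to the later visit, the overall shares would be 12/42 = 29% and 6/42 = 14%.
- Letting Visits 3 and 4 vary by ±2 days leaves vital signs at 33% overall (48% of ETs after Day 15).

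**Sensitivity to the assumed timing.**

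| ET timing (assumed) | Vital signs, all ETs | Vital signs, ETs after Week 2 | Laboratory, all ETs | Laboratory, ETs after Week 4 |
|---|---|---|---|---|
| Uniform | 33% | 50% | 17% | 50% |
| Exponential, mean 10 days | 16% | 67% | 3% | 67% |
| Exponential, mean 20 days | 25% | 59% | 8% | 59% |
| Exponential, mean 40 days | 30% | 54% | 12% | 54% |
| Rising triangular | 39% | 44% | 25% | 45% |
| Falling triangular | 28% | 63% | 8% | 75% |

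These timings all spread ETs over the treatment period. ETs clustered soon after Visit 3 or 4 would be hit harder: all of them if within 7 days of the visit, 70% if spread over 10 days, 50% if spread over 14.

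**Scale in patients (illustration).** With 300/2 = 150 per arm and an assumed 20% ET rate, there are 30 ETs per arm. Uniform timing displaces 30 × 14/42 = 10 vital-sign sets and 30 × 7/42 = 5 laboratory sets per arm. If each displaced laboratory value differed from the retained one by an assumed 0.5 SD, the Week 4 mean (N about 140) would move by 5 × 0.5/140 = 0.02 SD.

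**Efficacy.** A simulation of MADRS with dropout driven by the ET score, an assumed model with 400,000 patients per arm, gave a Week 6 effect of at most 0.03 points. The point is therefore confined to safety data.

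**The case against.** One record per visit with priority for the scheduled one is a clear, pre-specified convention, and the SAP's safety analysis is descriptive. Several points against a stronger claim stand.

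- **Size.** A reader might infer that about half of all ET vital signs are lost. That holds only for ETs after Week 2. The overall share would reach half under uniform timing only if baseline were also a window target, and SAP 8.1.3 names Weeks 2, 4 and 6 only.
- **Other routes.** A reader might infer that the values vanish from reporting. They do not. Laboratory values are listed with out-of-range results flagged (SAP 10.4), and vital signs are listed (10.5.1). Treatment-emergent, clinically significant laboratory abnormalities are recorded as adverse events (protocol 11.3.6) and so reach the tables in SAP 10.2. Events leading to discontinuation have their own tables (10.3). This cover is partial: it depends on a judgement of clinical significance, it misses smaller shifts by arm, and protocol 11.3.4 has no matching sentence for vital signs.
- **Direction.** A reader might infer that the tables understate drug effects. The documents do not show that displaced values are worse. Protocol 10.4.1 also lists administrative and patient-request withdrawals, and it wants the ET visit even after a drug lapse. Such a value may be off drug, and the retained scheduled value may then reflect exposure better.
- **Effect on means.** As illustrated, it is likely small.
- **CSFQ-14 as precedent.** It supports a last on-treatment row only, not a worst-value row. CSFQ-14 is scheduled after baseline only at Visit 5/ET, so this collision cannot arise there.

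SAP 10.1 does say that all safety data will be tabulated as well as listed. However, 10.4 and 10.5.1 define only by-visit or by-time-point tables, and the displaced record has no place in them.

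**Conclusion.** The gap is real but modest. On the plain wording of SAP 8.1.3, 10.4 and 10.5.1, an ET record taken up to about 7 days after an attended visit enters no vital-sign or laboratory value table. Under uniform ET timing this is about one third of all ET vital-sign sets (16-39% across the timings in the table) and about one sixth of all ET laboratory sets (3-25%). These shares rest on assumed timing and on attendance at the preceding visit. The rule and its reach follow from the text alone. The consequence is a risk that values at discontinuation are under-represented in the by-arm safety comparison, not a demonstrated bias. It does not threaten the efficacy result or the ECG tables. It merits a change because the remedy is almost free.

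**What to change.** Keep the SAP 8.1.3 rule unchanged for by-visit rows. Limiting it to efficacy data would leave by-visit safety tables with two records for one patient and no rule for choosing between them.

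In SAP 10.4 and 10.5.1, add a *last on-treatment value* row giving the actual value and change from baseline by arm. It should include ET records taken on treatment, as 10.5.4.2 already plans for CSFQ-14. State in the SAP what counts as on treatment relative to the last dose, so that ET records after a lapse are handled consistently. This brings the share of on-treatment ET values missing from these tables to zero.

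It would also help to state in 8.1.3 which visit an ET exactly on a midpoint day belongs to. A *worst post-baseline value* row that includes ET and unscheduled records is optional and needs a direction defined for each parameter.

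The data are already collected. The cost is SAP wording, some programming and slightly longer tables.

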8.1.4. Timing of Analyses

All final, planned analyses will be performed after the last participant has completed all study assessments, all relevant study data have been processed and integrated into the analysis database, and the database has been locked.

Any post-hoc, exploratory analyses completed to support planned study analysis, which were not identified in this SAP, will be documented and reported in appendices to the CSR. Any results from these unplanned analyses (post-hoc) will also be clearly identified in the text of the CSR.

8.1.5. Multiple Comparisons/Multiplicity

The overall type I error rate will be controlled at α =0.05 for the set of primary and key secondary endpoint comparisons using a serial gatekeeping approach.

At each step, if a p-value fails to meet the alpha threshold for significance, the process will be halted and all subsequent comparisons declared non-significant. This will continue with the same pattern through the endpoints in the order listed below:

The order of the analyses will be:

- Change from Baseline (Visit 2) in the MADRS total score at Week 6 (Primary)
- Change from Baseline (Visit 2) in the CGI-S score at Week 6
- Change from Baseline (Visit 2) in the SDS total score at Week 6

Although all p-values will be non-significant following the first to fail to meet its alpha threshold, p-values will be reported for all the above endpoints; they will be noted as descriptive for those following the first non-significant p-value.

8.1.6. Power and Sample Size

The sample size will be approximately 300 patients with MDD.

9. ENDPOINT EVALUATION

9.1. Primary Endpoint

[figure not shown]
The primary efficacy endpoint will be the change from baseline in the MADRS total score at Week 6.

The MADRS is a validated, 10-item, clinician-administered depression scale. It will be completed at Screening (Visit 1), Baseline (Visit 2) and after Weeks 2, 4, and 6 of treatment (Visits 3, 4, and 5, respectively). The 10 items measure the core symptoms and cognitive features of clinical depression. This scale has historically been used in drug treatment trials due to its particular sensitivity to detect treatment effects.

Patients with a Screening (Visit 1) MADRS score of $\geq 28, \geq 25$ at Baseline (Visit 2), and a $\leq 25\%$ decrease or increase in MADRS score from Screening (Visit 1) to Baseline (Visit 2) are eligible to be randomized.

9.1.1. Computation of the Primary Endpoint

Each item has a severity scale from 0 to 6, with higher scores reflecting more severe symptoms. Individual items will be summed to form an overall score (from 0 to 60). It is not anticipated that there will be any missing individual items since the raters will be instructed to complete all the assessments.

Continuous outcomes included in the list of key secondary outcomes will be handled as above. Seeds for the SAS procedures are given in appendix section 14.2.

9.1.2. Primary Analysis of the Primary Endpoint

Summary statistics (mean, SD, median, minimum, maximum) for the primary efficacy endpoint will be reported for the change from the Baseline to week 6 for each of the treatment groups. The change from Baseline will be analyzed in an MMRM model for each multiple imputation set with fixed effects of treatment, visit, baseline value, treatment by visit interaction, baseline by visit interaction and pooled site; an unstructured covariance matrix will be used. Sites with less than 5 patients will be pooled into a single site; this covariate may be removed from the model in the case of convergence issues. Least square means (LSMs), standard errors, and the LSM differences (treatment vs placebo) for each of the 20 MI repeats will be combined using SAS procedure MIANALYZE (Rubin, 1976) and 95% CIs and p-values will be reported for each. Denominator degrees of freedom will use the Kenward Rogers approach. Should the model with unstructured variance fail to converge using the default Newton-Raphson approach, the Fisher scores (via the SCORING option of the PROC MIXED statement) will be utilized. Should this also fail to converge, then other approaches as detailed in Lu 2010 will be utilized. Once these approaches have been exhausted, then the following structures will be used in order with the first to converge being selected: heterogeneous Toeplitz, heterogeneous first-order autoregressive, Toeplitz, first order autoregressive and compound symmetric will be attempted in that order; in these cases, the sandwich estimator (Diggle and Kenward 1994) will be used to estimate the standard errors of the fixed effects parameters and the denominator degrees of freedom will utilize the DDFM=BETWITHIN option in SAS®.

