5. ESTIMANDS FOR PRIMARY AND KEY SECONDARY EFFICACY ENDPOINTS

5.1. Primary Efficacy

Population

The target population is individuals with major depressive disorder as defined by the inclusion/exclusion criteria.

Variable

The primary endpoint will be the change from Baseline (Visit 2) to Week 6 in the MADRS total score.

Intercurrent Events

Concomitant medications and all other intercurrent events other than discontinuation will use a treatment policy strategy; data will be analyzed as observed. A hypothetical strategy will be employed to handle intermittent missing data and discontinuation. Patients that that discontinue for adverse events or lack of efficacy will be assumed to be representative of patients that would not continue treatment and their values will be imputed with multiple imputation (MI) using the placebo distribution. All other missing values, whether intermittent or following discontinuation will be assumed to be missing at random and imputed with MI within treatment group. See section 9.1.1 for details of the imputation.

Population-Level Summary

The population-level summary will be the difference in least-square means between treatment arms (analyzed as randomized) at Week 6.

The primary efficacy analysis will use a mixed model repeated measures (MMRM) approach to estimate mean change from baseline to Week 6 in the MADRS total score visit in the TNX-601 ER and placebo arms. The model will include all patients in the ITT population, and the dependent variable will be the observed change from baseline in the MADRS total score at each post-randomization in-clinic visit. Covariates in the model will include the fixed categorical effects of treatment, site, visit, and treatment by visit interaction, as well as the continuous fixed covariates of baseline score and baseline score by visit interaction. Full details are given in section 9.1.2.

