9.1.3.3. Multiple Imputation Tipping Point

A tipping point analysis will be performed using the primary analysis MI datasets (from section 9.1.2) and applying an increasing delta (of MADRS score) to the active group until statistical significance is no longer achieved. The delta will only be applied to imputed values; this will be done in 0.5 increments on the MADRS total score. This will only be performed if the primary analysis is significant. This will test the overall robustness of the primary analysis.

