9.2.1. Key Secondary Endpoints

There will be two key secondary endpoints:

9.2.1.1. Change from Baseline (Visit 2) in the CGI-S score at Week 6

The CGI-S score will be scored 1-7 and treated as a continuous variable. It will be analyzed in a manner identical to the primary endpoint (MMRM with MI using an MNAR approach for patients dropping for AEs and LOE).

Sensitivity analyses will include considering all patient dropouts as missing at random (paralleling the approach in section 9.1.3.1) and considering all patient dropouts as missing not at random (paralleling the approach in section 9.1.3.2).

9.2.1.2. Change from Baseline (Visit 2) in the SDS total score at Week 6

For participants that respond to all three questions (work, social life/leisure and home) on the SDS, their total score will be the sum of the three items. Participants that do not respond to the work/school item because they have not worked or attended school in the recall period for reasons unrelated to their disease state will not have that value imputed; to retain the 0 to 30 scaling for the total score, the participant's other two items will be summed and multiplied by 1.5. This approach reports the disease impact on the applicable domains. Due to the design of the ePRO, participants may both respond to the work/school item and check the box that they have not worked or attended school in the recall period for reasons unrelated to their disease state. In these instances, the checkbox will supersede the response and the 0-10 score will be censored; as above, the participant's other two items will be summed and multiplied by 1.5. Participants that have either of the other items missing or have work/school item missing but do not check the box to indicate that they did not work/attend school will be assigned a missing value.

The SDS total score will be analyzed in a manner identical to the primary endpoint (MMRM with MI using an MNAR approach for patients dropping for AEs and LOE).

Sensitivity analyses will include considering all patient dropouts as missing at random (paralleling the approach in section 9.1.3.1) and considering all patient dropouts as missing not at random (paralleling the approach in section 9.1.3.2).

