9.2.2. Exploratory Endpoints

9.2.2.1. Continuous Exploratory Endpoints

Each of the following continuous endpoints will be summarized:

- Change from Baseline (Visit 2) in the CGI-S score at Week 2 and Week 4
- Change from Baseline (Visit 2) in the SDS total score at Week 2 and Week 4
- Change from Baseline (Visit 2) in PGIS score at Weeks 2, 4, and 6
- Change from Baseline (Visit 2) to Week 6 in the CSFQ-14 total score in females and in males (analyzed separately)
- Change from Baseline (Visit 2) in the HARS total score at Weeks 2, 4, and 6
- Change from Baseline (Visit 2) in each of the 3 domains (work/school; social life; home life or family responsibilities) using the SDS at Weeks 2, 4, and 6
- Mean PGIC score at Weeks 2, 4, and 6
- Mean CGI-I score at Weeks 2, 4, and 6

The CGI-S score and SDS total score at Week 2 and Week 4 will be reported out of the same MMRM model used for each of these key secondary endpoints.

Statistical Analysis Plan: TNX-TI-M201

The PGIS, HARS total score, and SDS domains (work/school; social life; home life or family responsibilities) will be analyzed using a model identical to the primary efficacy endpoint, but on observed data only, without multiple imputation. Additionally, the primary efficacy and key secondary endpoints will be reported out of an MMRM without imputation.

The CSFQ-14 total score will be summarized with descriptive statistics and compared between groups with an ANCOVA with effects for treatment and baseline value.

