14.2. Random Seeds

The following list of numbers will be used for random seeds where required for MI processes:

54748395

35852537

55264123

85945257

84116945

34285262

13458178

72845657

28932945

95785785

These will generally be used in order for the primary analysis, then secondary endpoints and sensitivity analyses. For cases where identical code may be applied to more than one outcome or a sensitivity analysis that uses a minor variation on the primary code, the second to last digit will be incremented by 1 to produce new seeds for the subsequent outcome/analysis. If a single dataset requires more than the 10 seeds above, additional seeds will be generated by incrementing the last digit by 1. All seeds used will be documented in the programming specifications and the programs themselves.

Tonix Pharmaceuticals Statistical Analysis Plan: TNX-TI-M201

ATTACHMENTS 15.

N/A

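### With 20 imputations, simulation noise alone would change the MADRS, CGI-S or SDS verdict in about 1–4% of trials (dropout assumed); a larger number costs only computing time

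*SAP*

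**What the plan says.** SAP 9.1.2 fits the MMRM to each imputed dataset and pools the results by Rubin's rules: "LSM differences (treatment vs placebo) for each of the 20 MI repeats will be combined using SAS procedure MIANALYZE". For CGI-S, SAP 9.2.1.1 states "It will be analyzed in a manner identical to the primary endpoint", and SAP 9.2.1.2 states "The SDS total score will be analyzed in a manner identical to the primary endpoint". The number 20 therefore governs all three confirmatory tests.

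SAP 8.1.5 tests them in a fixed order (MADRS, CGI-S, SDS) at 0.05, and protocol section 13 makes this two-sided. At each step, "if a p-value fails to meet the alpha threshold for significance, the process will be halted and all subsequent comparisons declared non-significant".

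Under SAP 5.1, for patients who stop because of adverse events or lack of efficacy, "their values will be imputed with multiple imputation (MI) using the placebo distribution". Other missing values are imputed within arm as missing at random.

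Three further passages bear on the point:

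- SAP 9.1.3.3 reuses the same imputed data: "A tipping point analysis will be performed using the primary analysis MI datasets".
- SAP 14.2 lists ten seeds and says "These will generally be used in order for the primary analysis, then secondary endpoints and sensitivity analyses".
- SAP 9.2.2.1 adds a check that needs no random draw: "the primary efficacy and key secondary endpoints will be reported out of an MMRM without imputation".

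The visible text gives no reason for 20, no limit on Monte Carlo error and no expected dropout rate. Parts of SAP 9.1.1 and 8.1.6 appear to have been removed from the public copy, so their absence is not held against the plan. The number 20 itself is explicit in 9.1.2.

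**The concern.** With a finite number of imputations, both the pooled treatment difference and the between-imputation variance are simulation estimates. Run the same locked data with other seeds and the p-value moves. Pre-specified seeds fix which draw is used and largely prevent choosing among draws, but the one draw that is used is no more precise for that.

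For most outcomes the movement is irrelevant. It matters when the p-value falls near 0.05, because the primary verdict decides whether CGI-S is tested and the CGI-S verdict decides whether SDS is tested. An independent programmer with different seeds could then reach the opposite conclusion from identical data.

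**Working it through.** **Inputs.** From the documents: M = 20 imputations (SAP 9.1.2); two-sided 0.05 (protocol 13; SAP 8.1.5); about 300 patients randomized 1:1, so 150 per arm (SAP 7.2, 8.1.6); the imputation rule of SAP 5.1. Assumed, because not visible: dropout, SDs, visit correlations, true effect, and 40% of dropouts being for adverse events or lack of efficacy. The plan derives no figure here, so there is none to reproduce.

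**Step 1: how far the seed moves z.** Let g be the fraction of missing information, and scale the large-M variance to 1. Near z = 1.96 the SD of the pooled z over seeds is

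SD = √[ g/M + (1.96·g/2)² · 2/(M−1) ].

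For g = 0.15 and M = 20: √[0.0075 + 0.147² × 2/19] = √[0.0075 + 0.0023] = 0.099. For M = 500: √[0.00030 + 0.00009] = 0.020.

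**Step 2: how often the verdict changes.** The chance of disagreeing with an infinite number of imputations is about f × SD × √(2/π), where f is the density of z at the critical value. With no effect f = 0.117 (both tails); at 50%, 80% and 90% power it is 0.399, 0.280 and 0.175. For g = 0.15, M = 20 and 50% power: 0.399 × 0.099 × 0.798 = 3.15%.

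| g | M | SD of z | No effect | 50% power | 80% power | 90% power |
|---|---|---|---|---|---|---|
| 0.10 | 20 | 0.078 | 0.72% | 2.47% | 1.73% | 1.09% |
| 0.15 | 20 | 0.099 | 0.92% | 3.15% | 2.21% | 1.38% |
| 0.20 | 20 | 0.119 | 1.11% | 3.77% | 2.65% | 1.66% |
| 0.15 | 100 | 0.044 | 0.41% | 1.40% | 0.98% | 0.62% |
| 0.15 | 500 | 0.020 | 0.18% | 0.63% | 0.44% | 0.28% |

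**Step 3: direct simulation of the SAP 5.1 rule.** Assumptions: 150 per arm; baseline SD 4; change SD 7.5/8.5/9.0 at Weeks 2/4/6; visit correlations 0.5–0.75; monotone dropout. The analysis was a Week 6 ANCOVA on each completed dataset, pooled by Rubin's rules. On complete data this gives the same Week 6 contrast as the MMRM, apart from the omitted site term. There were 5,000 null trials and 2,500–3,000 per effect at each dropout level. The table shows disagreement between M = 20 and M = 1,000 (power in brackets):

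| Missing at Week 6 (g) | No effect | 2.2 points | 3.2 points | 3.7 points |
|---|---|---|---|---|
| 13% (0.09) | 0.6% | 2.5% (49%) | 1.6% (82%) | 0.8% (93%) |
| 21% (0.15) | 0.8% | 3.6% (47%) | 2.7% (78%) | 1.5% (89%) |
| 31% (0.22) | 1.0% | 4.4% (39%) | 4.2% (71%) | 2.8% (84%) |

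The simulation standard error of these rates is 0.07–0.25 percentage points. M = 500 and M = 1,000 disagree in 0.1–0.2% of null trials and 0.2–1.2% otherwise. The seed moves the estimate by 0.07–0.12 MADRS points, against a standard error of about 1.1.

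A second simulation used other assumptions: Week 6 SD 10, correlations 0.25–0.75, dropout 10–30% and g 0.07–0.19. It gave 0.4–0.7% with no effect and 1.3–4.5% at about 43–78% power.

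**Step 4: near the threshold.** Take a large-M p of 0.045 (z = 2.005) and g = 0.15. At M = 20 Rubin's variance grows by g/M = 0.0075, so z becomes 2.005/√1.0075 = 1.997. The degrees of freedom are about 19/0.15² = 844, so the critical value is 1.963. The margin is 0.034, or 0.34 SD at an SD of 0.100, which gives a flip rate of about 37%. Drawing the estimate and variance 400,000 times per cell gives:

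| Large-M p | M = 20, g = 0.10/0.15/0.20 | M = 500, same g |
|---|---|---|
| 0.045 | 31/36/40% | 0.2/1.3/3.0% |
| 0.04 | 13/20/25% | nearly zero |
| 0.06 | 14/19/22% | nearly zero |

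In the Step 3 simulation the M = 1,000 p-value lies between 0.03 and 0.07 in 3–4% of null trials and 6–16% of trials with an effect. Inside that zone 13–29% of M = 20 runs give the other verdict.

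**Step 5: interim combination.** Protocol 13.6 combines the data from before and after the interim by the Cui–Hung–Wang method. With 75 per arm per stage, separate imputation by stage, equal weights (assumed) and 21% missing, disagreement was 0.7% with no effect and 2.8% at 3.2 points. Without stages it was 0.8% and 2.7%.

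**The case against.** The strongest reply is that nothing here is invalid. Rubin's variance and degrees of freedom already allow for finite M. At g = 0.15 the added variance is 0.15/20 = 0.75%, and a seed SD of about 0.10 is small beside the sampling SD of about 1 for z. The seeds are listed in advance, so the planned analysis has one result that can be rerun exactly. Disagreement with a much larger M can go either way and is not a rate of wrong conclusions. With no effect it is at or below 1%, and rates above 4% need about 30% missing and moderate power. Conditional rates of 31–40% describe p-values that few trials produce. The MMRM without imputation and the planned sensitivity analyses would be read beside any borderline result.

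All of that stands, and it is why the point is minor. In the Step 3 simulation the M = 20 test rejected in 4.1/3.7/3.1% of null trials, which is somewhat conservative, so no type I inflation is claimed. I do not attribute that conservatism to the number of imputations or expect a larger number to remove it.

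It does not remove the point. A repeatable draw is still a noisy one. The MMRM without imputation is not the gatekeeping test, and it does not impute adverse-event and lack-of-efficacy dropouts from placebo. A figure of 500 is a preference: 100 already helps. In the second simulation, at 10–20% dropout, two seeds disagree at M = 100 in 0.2–0.3% of null trials and 0.7–2.3% at about 50–80% power. At M = 500 this falls to 0.1–0.2% and 0.3–1.1%.

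**Conclusion.** The concern holds, as a minor one. Under assumed dropout, using 20 imputations rather than a very large number would change the significance verdict in about 1–4% of trials overall. The lower end applies with no effect or high power, and the upper end with heavy dropout and moderate power. The chance is much larger when the p-value is close to 0.05. What is at stake is whether a borderline verdict, and the gate that depends on it, can be reproduced. Validity and the size of the estimated effect are not in question.

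The figures rest on assumed dropout, SDs, correlations and effects, on monotone dropout, and on an analysis without the site term. CGI-S and SDS were not simulated separately. Their rates are inferred from the same number of imputations and similar missingness, and they matter only if the gate is open.

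**What to change.** Before unblinding, replace the 20 in SAP 9.1.2 with a larger number, such as 500 or more. Because SAP 9.2.1 and 9.1.3.3 refer back to the primary analysis, the change carries over to CGI-S, SDS and the tipping point. State the same number for the imputation analyses in SAP 9.1.3.1 and 9.1.3.2 and their CGI-S and SDS counterparts. Keep the listed seeds, and report the Monte Carlo error of the pooled estimate and p-value so that a reader can see whether a borderline verdict depends on the draw.

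The cost is one number in the SAP, a reporting line and some computing time. No patients, data, estimand or missing-data assumptions change.
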